
For patients with normal baseline ALT and AST and total bilirubin value:
 
AST or ALT <math>> 3.0 \times</math> ULN combined with total bilirubin <math>> 2.0 \times</math> ULN without evidence of cholestasisc
 
OR
 
For patients with elevated baseline AST or ALT or total bilirubin value:
 
[AST or ALT <math>> 2 \times</math> baseline AND <math>> 3.0 \times</math> ULN] OR [AST or ALT <math>> 8.0 \times</math> ULN], whichever is lower, combined with [total bilirubin <math>> 2 \times</math> baseline AND <math>> 2.0 \times</math> ULN]
	Mandatory: Permanently discontinue patient from study drug treatment
METABOLIC	
Asymptomatic amylase and/or lipase elevation (If symptomatic elevations of any grade, discontinue INC280 permanently)	
Grade 1 ( $>$ ULN - $1.5 \times$ ULN)	Maintain dose level
Grade 2 ( $> 1.5 - 2.0 \times$ ULN)	Maintain dose level
Grade 3 ( $> 2.0 - 5.0 \times$ ULN)	Omit the dose until resolved to $\leq$ grade 2, then If resolved in $\leq$ 14 days, resume treatment at the same dose level If resolved in $>$ 14 days, then $\downarrow$ 1 dose level
Grade 4 ( $> 5.0 \times$ ULN)	Mandatory: Permanently discontinue patient from study drug treatment

Recommended dose modifications for INC280	
Worst toxicity CTCAE Grade a	During a cycle of therapy
CARDIAC	
Electrocardiogram QT corrected (QTc) interval prolonged	
Grade 1 (QTcF 450-480 ms) and Grade 2 (QTcF 481-500 ms) Grade 3 (QTcF $\geq$ 501 ms on at least two separate ECGs)	Maintain dose level  Omit dose until resolved to $\leq$ grade 2, then: If resolved in $\leq$ 7 days, resume treatment at the same dose level If resolved in $>$ 7 days, then $\downarrow$ 1 dose level Mandatory: Permanently discontinue patient from study drug treatment
Grade 4 (QTcF $\geq$ 501 or $>$ 60 ms change from baseline and Torsades de pointes or polymorphic ventricular tachycardia or signs/symptoms of serious arrhythmia)	
GASTROINTESTINAL	
Pancreatitis Grade 2 Grade $\geq$ 3	Maintain dose level Mandatory: Permanently discontinue patient from study drug treatment
Diarrhea** Grade 1 (despite maximal anti-diarrheal medication) Grade 2 (despite maximal anti-diarrheal medication)	Maintain dose level Omit dose until resolved to $\leq$ grade 1, then maintain dose level. If diarrhea returns as $\geq$ grade 2, then omit dose until resolved to $\leq$ grade 1, then resume treatment at $\downarrow$ 1 dose level

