Grade 2	
Mandatory: Interrupt INC280 dose during diagnostic workup for ILD until improvement to <math>\leq</math> Grade 1. Exclude infections and other etiologies.
 
In presence of diagnosis of ILD/Pneumonitis after diagnostic workup, it is mandatory to permanently discontinue INC280.
 
Only in absence of diagnosis of ILD/Pneumonitis, study drug may be restarted following these guidelines:
 
 
• If resolves to <math>\leq</math> Grade 1 in <math>\leq</math> 7 days reduce study drug by 1 dose level
 
• If fails to resolve to <math>\leq</math> Grade 1 within 7 days or recurs after resumption of study drug at decreased dose, permanently discontinue INC280
 

Grade 3 and Grade 4	Mandatory: Permanently discontinue study drug

Recommended dose modifications for INC280	
Worst toxicity CTCAE Grade a	During a cycle of therapy
	Treat with IV steroids as clinically indicated. Oxygen therapy as indicated.
Fatigue/ Asthenia (General disorders and administration site conditions)	
Grade 1 or 2	Maintain dose level
Grade 3	Omit dose until resolved to ≤ grade 1, then: If resolved in ≤ 7 days, resume treatment at same dose level If resolved in > 7 days, resume treatment at ↓ 1 dose level
Peripheral edema	
Grade 1 or 2	Maintain dose level
Grade 3	Discontinue dose until resolved to ≤ Grade 1, then ↓ 1 dose level
Other adverse events	
Grade 1 or 2	Maintain dose level, consider to initiate appropriate support medication. For any intolerable grade 2 (e.g.: limiting instrumental ADL), consider omitting the dose until resolved to ≤ grade 1, then ↓ 1 dose level.
Grade 3	Omit dose until resolved to ≤ grade 2, then ↓ 1 dose level
Grade 4	Omit dose and then discontinue from study drug treatment
All dose modifications should be based on the worst preceding toxicity. a Common Toxicity Criteria for Adverse Events (CTCAE Version 4.03).	
b "Combined" defined as: total bilirubin increase to the defined threshold concurrently with ALT/AST increase to the defined threshold	
c "Cholestasis" defined as: ALP elevation (> 2.0 x ULN and R value (ALT/ALP in x ULN) < 2.0) in patients without bone metastasis, or elevation of ALP liver fraction in patients with bone metastasis	

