- Shift tables using CTC grades to compare baseline to the worst post-baseline value for laboratory parameters with CTC grades
- Shift tables using low, normal, high (as well as low and high combined) classifications to compare baseline to the worst post-baseline value for laboratory parameters where CTC grades are not defined.
- New or worsened abnormalities for laboratory parameters based on CTC grade
- Trends of renal function parameters (creatinine, BUN) over time (baseline and selected on-treatment time-points, See [Table 4-6](#)) will be displayed via boxplots based on time windows and corresponding tables displaying the statistics used for the box plots by the selected time points.

The following lab parameters will be summarized by cohort:

- Hematology: absolute lymphocytes, absolute neutrophils, hemoglobin (anemia), WBC, platelet counts, absolute basophils, absolute eosinophils, absolute monocytes, hematocrit
- Biochemistry: alkaline phosphatase (ALP), SGPT (ALT), SGOT (AST), total bilirubin, amylase, potassium, sodium, creatinine, glucose (hypo only), phosphate, albumin, calcium, magnesium, creatinine, direct bilirubin, blood urea nitrogen (BUN), GGT, lipase.
- For bi-directional parameters, both hyper and hypo summaries will be presented.

The following laboratory parameters will be presented in listings and will not be summarized:

- Urinalysis: macroscopic panel (dipstick) (bilirubin, blood, glucose, WBC, pH, protein, specific gravity), Urinalysis Microscopic panel (RBC, WBC, casts).
- Coagulation: INR, pro-thrombin time (PT) or Quick Test

The following listings will be produced for the laboratory data for all laboratory parameters where CTC grades are defined:

- Listing of patients with laboratory abnormalities of CTC grade 3 or 4
- Listing of all laboratory data with values flagged to show the corresponding CTC grades and the classifications relative to the laboratory reference ranges.

Liver function parameters of interest are total bilirubin (TBIL), ALT, AST and alkaline phosphatase (ALP). The number (%) of patients with worst post-baseline values will be summarized by cohort in the following categories:

- ALT >3×ULN, >5×ULN, >8×ULN, >10×ULN, >20×ULN
- AST >3×ULN, >5×ULN, >8×ULN, >10×ULN, >20×ULN
- ALT or AST >3×ULN, >5×ULN, >8×ULN, >10×ULN, >20×ULN
- TBIL > 2×ULN, >3×ULN

Combined and concurrent values post-baseline

- ALT or AST > 3×ULN & TBIL > 2×ULN
- ALT or AST > 3×ULN & TBIL > 2×ULN & ALP \geq 2×ULN

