- ALT or AST > 3×ULN & TBIL > 2×ULN & ALP < 2×ULN

Combined elevations values post-baseline (regardless of baseline levels)

- ALT or AST > 3×ULN & TBIL > 2×ULN
- ALT or AST > 3×ULN & TBIL > 2×ULN & ALP \geq 2×ULN
- ALT or AST > 3×ULN & TBIL > 2×ULN & ALP < 2×ULN

Combined elevations values post-baseline by baseline levels

AST/ALT \leq ULN at baseline

- ALT or AST > 3×ULN & TBIL > 2×ULN
- ALT or AST > 3×ULN & TBIL > 2×ULN & ALP \geq 2×ULN
- ALT or AST > 3×ULN & TBIL > 2×ULN & ALP < 2×ULN

AST/ALT > UNL at baseline

- Elevated ALT or AST & TBIL (>2×Baseline and 2×ULN)
- Elevated ALT or AST & TBIL (>2×Baseline and 2×ULN) & ALP \geq 2×ULN
- Elevated ALT or AST & TBIL (>2×Baseline and 2×ULN) & ALP < 2×ULN

with Elevated AST or ALT defined as: >3×ULN if \leq ULN at baseline, or (>3×Baseline or 8×ULN) if > ULN at baseline

In addition, a listing of all TBIL, ALT, AST and ALP values for patients with a post-baseline TBIL > 2×ULN, ALT > 3×ULN or AST > 3×ULN will be provided.

The relationship between post-baseline increases in ALT/AST and total bilirubin will be shown using eDISH plot: peak values of Total bilirubin vs peak values of ALT/AST at any time during the course of treatment (not necessarily concurrent).

Analysis of time to first occurrence of grade 3/4 AST/ALT (whichever occurs first) will be done. Time to first occurrence of grade 3/4 AST/ALT and duration of the first occurrence of grade 3/4 AST/ALT will be summarized using Kaplan-Meier method. Patients with grade 3/4 AST/ALT at baseline will be excluded from the analysis. Median together with 95% CI as well as 25th and 75th percentiles will be presented. In addition, the median time to occurrence for the subset of patients who experienced the event of interest will be calculated. Simple descriptive statistics

(median, min and max, 25th and 75th percentiles) will be presented. The probabilities at selected time points and the associate 95% CI will also be summarized.

Duration of first occurrence of grade 3/4 AST/ALT will be presented for the subset of patients who experienced the event. Median together with 95% CI as well as 25th and 75th percentiles will be presented.

ECGs

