4.7.1 Multiple assessments within post-baseline visits

For all analyses regarding abnormal assessments or analyses based on worst or best post-baseline value (laboratory, ECGs, vital signs, ECOG performance status), all post-baseline values will be included (scheduled, unscheduled, repeat). All unscheduled and repeat measurements will be included in listings.

Laboratory Data

For laboratory data, assessments can be collected from both local and central laboratory on the same date. For shift tables using CTC grades to compare baseline to the worst post-baseline value, the assessment with worst post-baseline value is used for analyses irrespective of the source. For LFT summaries, where concurrent measurements are used in the calculation of number and percentage of patients with worst post-baseline values, the assessment with worst post-baseline value is used (since worst values are based on the largest ratio of lab value to its ULN for each patient) although the worst values for the different parameters may be coming from different laboratories.

ECGs

For all patients, 3 ECGs are targeted to be measured at the protocol-defined (nominal) time-points. If a patient has more than one measurement at a nominal scheduled time point, the average of all available measurements associated with the nominal time point will be used for the analyses. For unscheduled visits, measurements taken within 15 min interval will also be averaged and used for analysis.

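### The SAP's by-baseline combined liver rows do not match the protocol's potential-DILI laboratory criterion, so no row isolates the patients who meet it

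*SAP*

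**What the plan says.** **Protocol, Table 6-3 and Section 6.3.4.1.** Two baseline groups are defined.

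- ALT, AST and total bilirubin (TBIL) all normal at baseline: ALT or AST above 3×ULN together with TBIL above 2×ULN.
- Any of the three raised. Table 6-3 words this group as "For patients with elevated baseline AST or ALT or total bilirubin value". The enzyme limit is twice baseline and also 3×ULN, or 8×ULN, whichever is lower. TBIL must exceed both twice baseline and 2×ULN.

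Footnote b of Table 6-3 explains what a combined elevation means: "total bilirubin increase to the defined threshold concurrently with ALT/AST increase to the defined threshold".

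**SAP 2.8.2, Laboratory data.** There are three blocks of combined rows, each split further by ALP at 2×ULN.

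- "Combined and concurrent values post-baseline": ALT or AST above 3×ULN with TBIL above 2×ULN, with no baseline adjustment.
- The same limits regardless of baseline, without the word concurrent.
- "Combined elevations values post-baseline by baseline levels". With AST/ALT at or below ULN, the limits are again 3×ULN and 2×ULN. Under "AST/ALT > UNL at baseline" (read here as ULN), TBIL must exceed twice baseline and 2×ULN, and an enzyme counts as elevated by "or (>3×Baseline or 8×ULN) if > ULN at baseline".

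SAP 4.7.1 adds a handling rule that begins "For LFT summaries, where concurrent measurements are used in the calculation of number and percentage of patients with worst post-baseline values", but does not say which rows those are.

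**The concern.** Hepatotoxicity is an adverse event of special interest. Among the combined-elevation rows, only the by-baseline block takes a raised starting value into account, so a reader of the report will naturally set it beside the protocol's own baseline-adjusted criterion. If the limits and strata differ, the two counts describe different patients, and the SAP gives no reason for the difference.

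Eligibility admits the baselines at which the definitions part. Protocol 5.2, criterion 7, allows ALT and AST up to 3×ULN (5×ULN with liver metastasis) and TBIL up to 1.5×ULN.

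**Working it through.** There is no figure in the plan to reproduce; the check compares two definitions. All values are multiples of ULN. Let b be the baseline of the enzyme concerned and t the baseline TBIL. The SAP's enzyme limit is read as satisfied when either part is met.

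**1. Enzyme cut-off when b > 1**

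- Protocol: min(max(2b, 3), 8)
- SAP by-baseline row: min(3b, 8)

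| b | Protocol | SAP | Gap |
|---|---|---|---|
| 1.1 | 3.0 | 3.3 | 0.3 |
| 1.5 | 3.0 | 4.5 | 1.5 |
| 2.0 | 4.0 | 6.0 | 2.0 |
| 2.67 | 5.33 | 8.0 | 2.67 |
| 3.0 | 6.0 | 8.0 | 2.0 |
| 3.5 | 7.0 | 8.0 | 1.0 |
| 4.0 and above | 8.0 | 8.0 | 0 |

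The SAP limit is higher throughout 1 < b < 4 and the limits coincide from b = 4. For b ≤ 1 both give 3, because 2b ≤ 2 is below 3. In this stratum the TBIL limits are identical, so on a single date the row can only under-count.

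**2. TBIL cut-off with normal AST/ALT and raised TBIL (t > 1)**

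- Protocol: max(2t, 2) = 2t
- SAP row for AST/ALT at or below ULN: 2

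| t | Protocol | SAP |
|---|---|---|
| 1.1 | 2.2 | 2.0 |
| 1.25 | 2.5 | 2.0 |
| 1.5 | 3.0 | 2.0 |

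The enzyme cut-off is 3 in both, so on a single date this stratum can only over-count.

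**3. The concurrent block**

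The protocol's enzyme cut-off is never below 3 and its TBIL cut-off never below 2. With the same concurrency rule, every protocol-positive patient therefore falls in the concurrent block. So do others, for example baseline ALT 2 with ALT 3.5 and TBIL 2.5: this passes 3 and 2 but not the protocol's 4.

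**4. Constructed example, ALT and TBIL on one date**

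| Patient | Baseline ALT, TBIL | Later ALT, TBIL | Protocol | SAP by-baseline | Concurrent block |
|---|---|---|---|---|---|
| A | 2, 0.8 | 3.5, 2.5 | no (needs ALT > 4) | no (needs ALT > 6) | yes |
| B | 2, 0.8 | 5, 2.5 | yes | no (needs ALT > 6) | yes |
| C | 2, 0.8 | 7, 2.5 | yes | yes | yes |
| E | 0.8, 1.4 | 4, 2.5 | no (needs TBIL > 2.8) | yes | yes |

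The protocol count is 2 (B, C), the by-baseline count is 2 (C, E) and the concurrent block is 4. Equal totals here hide different patients.

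**5. Timing**

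Suppose patient D, baseline ALT 2 and TBIL 0.8, has ALT 7 with TBIL 0.8 on one date and TBIL 2.5 with ALT 2 on a later one. D is not protocol-positive under footnote b. D enters the by-baseline rows only if those rows may pair values from different dates, which the SAP neither says nor rules out.

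**The case against.** The strongest reply is that nothing required is missing. Protocol 10.5.3.3 asks for CTCAE shift tables and listings, not for this table, and the SAP never claims that its by-baseline rows tabulate the potential-DILI criterion. The protocol limits guide action for a patient; the SAP rows are descriptive. This stands: the point is an inconsistency between definitions, not a departure from a protocol-specified analysis.

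Four stronger readings are tempting and are not supported.

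- *That these patients go uncounted or are lost.* The concurrent block includes all of them. The SAP lists all liver values for anyone with TBIL above 2×ULN or ALT or AST above 3×ULN, and Section 6.3.4.1 has confirmed cases with no alternative cause reported as SAEs. What is missing is a row that isolates them.
- *That the SAP ignores baseline bilirubin.* The raised-AST/ALT rows use the protocol's TBIL limits. Only the split and the rows at or below ULN leave baseline TBIL out.
- *That the by-baseline rows pair peaks from different dates.* Only one block carries the concurrent label, but SAP 4.7.1 speaks of concurrent liver summaries without naming the rows. This is an ambiguity, not a shown error.
- *That aligned rows would give the number who triggered permanent discontinuation.* Cholestasis also enters that decision in Table 6-3 and Section 6.3.4.1, and a laboratory row does not apply it.

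It may also be said that baseline is handled elsewhere, in the CTC shift tables and the summary "New or worsened abnormalities for laboratory parameters based on CTC grade". Those treat one parameter at a time and cannot show a combined elevation.

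**Conclusion.** The mismatch holds on two legs, and both stand even if every row is concurrent.

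- The enzyme cut-off is higher in the SAP for baselines strictly between 1 and 4×ULN. The largest gap is 2.67×ULN, at a baseline of 2.67×ULN. The effect is an under-count.
- The strata omit raised TBIL with normal AST/ALT. The TBIL limit is then lower than the protocol's by up to 1.0×ULN at the eligibility limit of 1.5×ULN. The effect is an over-count.

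The unstated timing is a third matter, to be clarified. Applying footnote b's meaning to Section 6.3.4.1 is an inference from the shared thresholds.

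The by-baseline total can therefore err in either direction against the protocol's laboratory criterion. The documents give no joint distribution of baseline and on-treatment values, so neither the number of patients affected nor the change in the reported count can be stated. No efficacy result or decision rule depends on this; it is a minor safety-reporting point. No view is taken on which threshold is clinically right.

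**What to change.** Reconcile the passages in one of two ways: align the by-baseline rows with the protocol's stated criterion, or keep them and add rows that tabulate it. The rows should:

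- use the protocol's ALT/AST and TBIL limits as written;
- use its strata: AST, ALT and TBIL all normal at baseline, against any of the three raised;
- state that they follow the same concurrency rule as the concurrent block, and set that rule out, since neither document gives a window;
- keep the existing split by ALP at 2×ULN;
- be labelled as laboratory-criterion counts that are neither confirmed DILI cases nor the discontinuation-trigger count, because cholestasis, repeat testing and alternative causes are not applied.

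The cost is one derivation and a few table rows, with no new data. The resulting counts may be higher or lower than those from the present by-baseline rows. The regardless-of-baseline rows, the listing and the eDISH plot are unaffected.

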2.8.4 Pharmacokinetics

Not applicable.

2.8.5 Pharmacogenetics/pharmacogenomics

Not applicable.

2.8.7 PK/PD

Not applicable.

2.9 Sample size calculation

Approximately 456 patients (69 patients per cohort in Cohorts 1a, 1b, 2, 3, 4 and 27 patients per each Cohort 5a, 5b, approximately 30 patients in Cohort 6 and approximately 27 patients in Cohort 7) will be enrolled in the study if none of the cohorts 1-4 is stopped for futility at the time of the interim analysis. The exact 95% CIs for various sample sizes and observed ORRs in each cohort 1-4 are shown in [Table 2-4](#) and in [Table 2-5](#) for cohorts 5a, 5b and 7.

Table 2-4 **Exact Binomial 95 percent Confidence Intervals for Various Sample Sizes and Observed ORRs in Each Cohort**

Sample size (N)	Number of responders	Observed ORR (%)	95% exact CI (%)
65	23	35.4	23.9
66	24	36.4	24.9
67	24	35.8	24.5
68	24	35.3	24.1
69	25	36.2	25.0
70	25	35.7	24.6
71	25	35.2	24.2
72	26	36.1	25.1

Table 2-5 **Exact Binomial 95 percent Confidence Intervals for Various Sample Sizes and Observed ORRs in each cohort 5a, 5b and 7**

Sample size (N)	Number of responders	Observed ORR (%)	95% exact CI (%)
25	14	56.0	34.9
26	15	58.0	36.9
27	15	55.6	35.3
28	16	57.1	37.2
29	16	55.2	35.7

The operating characteristics (with 69 patients per cohort in 1a, 1b, 2, 3 and 4) are shown in [Table 2-6](#) and [Table 2-7](#). The tables show probability of stopping at interim, probability for positive conclusion (i.e., not stopped at IA for futility and success criteria met at final analysis) and negative conclusion (i.e., not stopped at IA for futility but success criteria not met at final analysis) under different underlying true ORR. The operating characteristics (with 27 patients per cohort in 5a, 5b and 7) are shown in [Table 2-8](#). The table shows the probability of meeting the success criteria under different underlying true ORR.

Cohort 1a, Cohort 1b, Cohort 2 and Cohort 4

The operating characteristics at this sample size have $> 50\%$ probability of stopping the trial for futility when the true ORR is $< 25\%$. Also, when the true ORR is 35% then the probability of positive conclusion at the final analysis with 69 patients is $\geq 44\%$. If the true ORR is 45% or higher, the probability of positive conclusion at the final analysis with 69 patients is $> 90\%$.

Table 2-6 Operating Characteristics for Cohort 1 (MET GCN ≥ 6) and Cohort 2 (MET GCN ≥ 4 and < 6)

True ORR (%)	Probability of a cohort to stop at IA* (%)	Probability for positive conclusion in final analysis for a cohort (%)	Probability for negative conclusion in final analysis for a cohort (i.e. not stop at IA* and success criterion not met at final analysis) (%)
10	99.50	0.00	0.50
20	81.82	0.12	18.06
25	59.97	2.34	37.68
30	36.48	15.01	48.51
35	18.21	44.00	37.79
40	7.40	75.38	17.22
45	2.42	93.11	4.47
50	0.63	98.73	0.64

*Assuming interim analysis at 28 evaluable patients

Cohort 3 (MET GCN < 4)

The operating characteristics at this sample size have $> 60\%$ probability of stopping the trial for futility when the true ORR is $< 25\%$. With 69 patients and 20 evaluable patients for interim analysis, when the true ORR is 10% then the probability of stopping for futility at the interim analysis is $> 90\%$. If the true ORR is 20% , the probability of stopping for futility at the interim analysis is $> 80\%$ and the probability of positive conclusion at the final analysis is $< 1\%$.

Table 2-7 Operating Characteristics for Cohort 3 (MET GCN < 4)

True ORR (%)	Probability of a cohort to stop at IA* (%)	Probability of positive conclusion in final analysis for a cohort (%)	Probability of negative conclusion in final analysis for a cohort (i.e., not stop at IA* and success criterion not met at final analysis) (%)
10	98.87	0	1.13
20	80.42	0.11	19.47
25	61.72	2.17	36.12

True ORR (%)	Probability of a cohort to stop at IA* (%)	Probability of positive conclusion in final analysis for a cohort (%)	Probability of negative conclusion in final analysis for a cohort (i.e., not stop at IA* and success criterion not met at final analysis) (%)
30	41.64	13.98	44.39
35	24.54	41.41	34.05
40	12.56	71.99	15.45
45	5.53	90.46	4.01
50	2.07	97.36	0.57

*Assuming interim analysis at 20 evaluable patients

Cohort 5a, 5b and 7

The operating characteristics at this sample size of 27 have < 36% probability of the trial meeting the success criteria when the true ORR is $\leq 50\%$. If the true ORR is $\geq 60\%$, the probability of the trial meeting the success criteria is $\geq 75\%$.

Table 2-8 Operating Characteristics for Cohort 5a, 5b and 7

Sample size (N)	True ORR (%)	Probability (%) that ORR $\geq 55\%$ with lower 95% CI $> 35\%$
27	40	7.4
27	45	18.1
27	50	35.1
27	55	55.6
27	60	75.0
27	65	88.9

Cohort 6

In expansion Cohort 6, patients with either MET GCN ≥ 10 without MET mutations or MET mutations regardless of MET GCN will be enrolled. Based on the rarity of this patient population and considering recruitment within a reasonable timeframe, approximately 30 patients are expected to be enrolled in Cohort 6.

Data from Cohort 6 will help further characterize the safety and efficacy of INC280 in the pre-treated population (from Cohort 1a and Cohort 4).

